**PAGE 42 OF 287** 

AE=Adverse Event; AESI=Adverse Event of Special Interest; CAJIS=Cumulative Analogue Joint Involvement Scale; CT= Computed Tomography; DLCO=Diffusion Capacity of the Lung for Carbon Monoxide; FEV1=Forced Expiratory Volume in one second; FOP=Fibrodysplasia Ossificans Progressiva; FOP-PFQ=FOP-Physical Function Questionnaire; FVC=Forced Vital Capacity; HEENT= head, eyes, ears, nose and throat; PI=Prescribing Information; PROMIS=Patient-Reported Outcomes Measurement Information System; SAE=Serious Adverse Event.

- a Follow-up Visits are recommended every 6 months, or as per local label.
- b If participant <18 years (or the legal age of consent in the jurisdiction in which the study is taking place), assent and parent or legally authorised representative consent will also be required.
- c This includes a general assessment, dermatologic, lymph nodes, HEENT, chest, cardiac, abdomen, limb/extremities, musculoskeletal, neurologic and other.
- d Not expected in the context of a telephone/video visit.
- e Collected for growing children. Assessment as per local label.
- f Linear height within 6 to 12 months prior to first marketed palovarotene intake.
- g Vital signs to be collected are respiratory rate, blood pressure and heart rate.
- h Participants will be assessed for child-bearing status and pregnancy prevention measures. As per local label, pregnancy testing is carried out with a confirmation of absence of pregnancy monthly if the participant receives palovarotene and one month after stopping. These conditions also concern participants who are not currently sexually active unless the prescriber considers that there are compelling reasons to indicate that there is no risk of pregnancy.
- This includes a period of two months prior to the first marketed palovarotene intake.
- j Not applicable for pregnant participants.
- k Spirometry obtains the lung function parameters of observed and % predicted FVC and FEV1 and the absolute and % predicted FEV1/FVC ratio. The DLCO test obtains observed and % predicted DLCO which provides information on the efficiency of gas transfer from alveolar air into the bloodstream.
- 1 This includes number of flare-ups over the past 12 months before the first marketed palovarotene intake.
- m Spinal health assessment to be performed using radiological imaging (e.g. CT, X-ray, scintigraphy, etc).
- n AE, SAE, Special Situation and AESI collection begins once the informed consent has been signed.
- o Paper-based patient-reported questionnaires.
- p Retrospective data collected only at the first marketed palovarotene intake.

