**PAGE 30 OF 287** 

#### 7.3.1 Safety Profile of Palovarotene

Safety data from the FOP clinical studies reflect exposure to palovarotene in a total of 164 participants, including 139 participants aged 8 years and above for females and 10 years and above for males ( $\geq 8/10$  years; the target population for the FOPal registry study) for a mean duration of 94.1 weeks, to a maximum of 3.8 years. Participants received either:

- Chronic/flare-up regimen 5 mg daily dose of palovarotene with a 20/10 mg dose for 12 weeks at the time of flare-up (4 weeks of 20 mg once daily followed by 10 mg once daily for 8 weeks);
- Flare-up regimen of either the 20/10 mg dose for 12 weeks, a 10/5 mg dose for 6 weeks (10 mg once daily for 2 weeks followed by 5 mg once daily for 4 weeks) or a 5/2.5 mg dose for 6 weeks (5 mg once daily for 2 weeks followed by 2.5 mg once daily for 4 weeks).

In palovarotene-exposed participants aged  $\geq 8/10$  years, the most commonly reported adverse reactions were in the *Skin and subcutaneous disorders* (97.8%), *Gastrointestinal disorders* (75.5%) and *Infections and infestations* (48.9%) System Organ Classes (SOC).

Participants <18 years with open epiphyses were assessed for growth during the clinical studies. PPC was identified in 27 of 102 participants (26%) <18 years of age and was more common in younger (<8/10 years: 14 of 25 participants, 56%) compared with older ( $\geq$ 8/10 to <14 years: 13 of 39 participants, 33%; and  $\geq$ 14 to <18 years: 0 of 38 participants, 0%) participants. In participants who received only chronic dosing, PPC, when observed, typically occurred between 12 and 18 months. The higher proportion of younger participants with PPC is not unexpected given that pre-adolescent individuals are not expected to have physiological growth plate closure. Thus, any narrowing, partial closure, or closure are likely to be assessed as premature by the clinician. However, the possibility that younger participants are predisposed to developing PPC or are more sensitive to the effects of palovarotene cannot be excluded.

Palovarotene treatment is currently indicated for children aged 8 years and above for females and 10 years and above for males (or as per the approved indication in locally approved label). However, children between the ages of 4 years and 8/10 years were included in the clinical studies and exposed to palovarotene. The safety profile for palovarotene in participants with

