**PAGE 41 OF 287** 

 Table 3
 Schedule of Assessments: Exposed Non-naïve Participants

Assessment/Procedure	Retrospective Period (From first marketed palovarotene intake)	Baseline Visit	Follow-Up Visits (as per routine clinical practice[a])/ End of Study Visit
Clinic visit or telephone/video contact visit		X	X
Informed consent [b]		X	
Inclusion/exclusion criteria		X	
Baseline demographics		X	
Physical examination [c,d]	X [p]	X	X
Medical or surgical history	X		
FOP history	X		
Growth status assessment (bone age, knee height and epiphyseal status) [d,e]	X [p]	X	X
Tanner staging	X [p]	X	X
Linear height [f] and weight [d]	X	X	X
Vital signs [d,g]	X [p]	X	X
Pregnancy testing [h]		X	X
Prior /concomitant medications [i]	X	X	X
Concomitant surgery and non-drug therapies	X	X	X
Prior use of palovarotene (investigational product)	X		
Palovarotene dose for chronic and flare-up treatment [j]	X	X	X
Spirometry and DLCO test [d,k]	X [p]	X	X
CAJIS [d]	X [p]	X	X
Movement mobility history (including flare-ups [l])	X		
Movement mobility changes (including flare-ups)		X	X
Spinal health assessment [m]	X [p]		X
Retrospective important medical events related to the disease (including vertebral fractures)	X		
AEs SAEs, Special Situations and AESIs [n]		X	X
Participant Questionnaires:			·
FOP-PFQ assessment [o]		X	X
PROMIS Global Health Scale [o]		X	X
FOP assistive devices assessment [o]		X	X

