#### For exposed non-naïve participants (Table 3):

- Baseline demographics;
- Physical examination including a general assessment as well as dermatologic, lymph nodes, HEENT, chest, cardiac, abdomen, limb/extremities, musculoskeletal, neurologic and other assessments (as per routine clinical care);
- Medical or surgical history (12 months before the first marketed palovarotene intake);
- FOP history (date of symptom onset, date of diagnosis by a physician, method of diagnosis, date of genetic test if performed and type of FOP genetic variant);
- Growth status assessment for growing children (bone age, knee height and epiphyseal status assessment) at the first marketed palovarotene intake and at the Baseline Visit;
- Tanner staging for growing children at the first marketed palovarotene intake and at the Baseline Visit:
- Linear height and weight from the first marketed palovarotene intake and at the Baseline Visit (linear height within 6 to 12 months prior to the first marketed palovarotene intake will also be collected);
- Vital signs (respiratory rate, blood pressure and heart rate);
- Pregnancy test (as per local label, participants are assessed for child-bearing status and pregnancy prevention measures. These conditions also concern participants who are not currently sexually active unless the prescriber considers that there are compelling reasons to indicate that there is no risk of pregnancy);
- Prior (two months prior to the first marketed palovarotene intake and until the Baseline Visit) and concomitant medications;
- Concomitant surgery and non-drug therapies;
- Prior use of palovarotene (investigational product);
- Marketed palovarotene dose for chronic and flare-up treatment;
- Spirometry and DLCO test at the first marketed palovarotene intake and at the Baseline Visit:

PAGE 47 OF 287

- CAJIS for FOP at the first marketed palovarotene intake and at the Baseline Visit;
- Movement mobility history, including flare-ups (over the past 12 months prior to the first marketed palovarotene intake and until Baseline Visit);
- Movement mobility changes, including flare-ups (from Baseline Visit);
- Spinal health assessment using radiological imaging (e.g. CT, X-ray, scintigraphy, etc) at the first marketed palovarotene intake and at the Baseline Visit;
- Retrospective important medical events related to the disease (including vertebral fractures) at the first marketed palovarotene intake and until the Baseline Visit;

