#### **Growth Status**

The FOPal registry study will collect bone age, knee height and epiphyseal status ("open/partially closed/closed/not assessable") for growing children at the Baseline Visit, at the first marketed palovarotene intake (for exposed non-naïve participants) and at the Follow-up/End of Study Visits if available.

Growing children are those in whom the growth plates have not fused. Whether the participant is a growing child is based on the investigator's assessment.

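### For children already on palovarotene at consent, growth-plate status, bone age, knee height and Tanner stage between first intake and Baseline are not collected, and the retrospective event row does not name PPC

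*Protocol*

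**What the plan says.** Table 3 is the schedule for exposed non-naïve participants. In its retrospective column, the growth-status and Tanner rows carry note p: "Retrospective data collected only at the first marketed palovarotene intake". Section 9.2.7.1 repeats the restriction for growth status: "Growth status assessment for growing children (bone age, knee height and epiphyseal status assessment) at the first marketed palovarotene intake and at the Baseline Visit". It words Tanner stage in the same way.

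Linear height is handled differently. Its row has no note p, and Section 9.2.7.1 asks for "Linear height and weight from the first marketed palovarotene intake and at the Baseline Visit".

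Section 7.3.1 gives the background. Under chronic-only dosing, "PPC, when observed, typically occurred between 12 and 18 months". Across the clinical studies, "PPC was identified in 27 of 102 participants (26%) <18 years of age".

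Growth status is collected for growing children (Table 3, note e). Section 9.3.2.7 defines them: "Growing children are those in whom the growth plates have not fused". It continues, "Whether the participant is a growing child is based on" the investigator's assessment, and gives no date at which this is judged. Section 9.7.3.4 summarises PPC among growing children.

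**The concern.** PPC frequency, severity and detail form a secondary endpoint, and PPC is one of the listed adverse events of special interest. The time between first intake and consent is analysed exposure time. Section 9.7.3.2 counts treatment-emergent events from the first marketed dose, and Section 9.7.3.4 sets the index date for exposed participants, naïve or not, at first marketed intake. For a child who consents late, that stretch can include the months in which PPC typically appeared, yet no serial growth-plate values are collected for it.

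Two further effects follow.

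- The height analyses stop at final adult height, defined either by a height velocity below 1 cm/year or by a closed epiphysis (Section 9.7.3.4). Heights from the gap are collected without the epiphyseal readings that the second criterion needs.
- Annualised height velocity needs consecutive measurements 6 to 12 months apart. If that rule also governs knee height, a child whose first intake and Baseline lie more than 12 months apart has no pre-Baseline knee-height velocity.

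A later analysis plan cannot recover values that the case report form never requested.

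**Working it through.** **1. The plan's own PPC figures (Section 7.3.1).** The age bands add up: 14 + 13 + 0 = 27 cases and 25 + 39 + 38 = 102 children. 27/102 = 26.5%, printed as 26%. By band: 14/25 = 56%, 13/39 = 33.3%, 0/38 = 0%. The registry admits only girls from 8 and boys from 10 years, so the relevant figure under 18 is 13/(39 + 38) = 13/77 = 16.9%.

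**2. Share of the 12–18 month window before consent.** Let T be months from first marketed intake to consent, and assume onset uniform over the window:

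share = min(max((T − 12)/6, 0), 1)

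| T (months) | Window before consent | Share |
|---|---|---|
| 12 or less | 0 of 6 months | 0% |
| 15 | 3 of 6 months | 50% |
| 18 or more | 6 of 6 months | 100% |

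The protocol does not give the distribution of T. It does allow patients treated before the registry opened in their country to enrol (Section 9.1), over an enrolment period of up to 10 years (Section 9.2.4), so long intervals are possible.

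**3. Scale.** About half of the minimum 67 exposed participants are to be paediatric (Section 9.5): 67/2 = 33.5. Expected PPC cases = 33.5 × 13/77 = 5.7, or 33.5 × 13/39 = 11.2 if every child were in the younger eligible band. Let f be the share of exposed children already past month 18 at consent, which is an assumption:

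| f | Cases at 16.9% risk | Cases at 33.3% risk |
|---|---|---|
| 0% | 0 | 0 |
| 25% | 1.4 | 2.8 |
| 50% | 2.8 | 5.6 |
| 75% | 4.2 | 8.4 |
| 100% | 5.7 | 11.2 |

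These are expected cases among children without serial growth-plate data over the window. They are not a count of cases missed.

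**4. What else captures PPC before consent.**

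- The retrospective important medical events row of Table 3 has no note p. Sections 9.3.2.5 and 11.2.1 run it from first marketed intake to consent, and Section 11.2.2 treats retrospective serious events and events of special interest as falling under it. Section 11.1.2 makes PPC serious by rule.
- That row's title refers to disease-related events and gives only vertebral fractures as an example. Table 3 note n starts collection of events of special interest at consent. Section 9.3.2.7 makes explicit retrospective provision for fractures in non-naïve participants, with no counterpart for PPC.
- For unexposed participants, Section 9.3.2.6 names PPC within the growth outcomes to be collected over the 12 months before consent. Retrospective PPC is thus named for the comparator and not for the treated children.

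**The case against.** A reader might infer that PPC before consent is lost altogether, that its timing is lost, and that the reported frequency is therefore biased downwards. The documents do not support this. A PPC diagnosed before consent belongs among the retrospective important medical events, and the adverse event items in Section 9.3.2.5 include start and end dates and time to onset. Epiphyseal status at first intake and at Baseline, where recorded, also brackets any closure. Downward bias is possible but not shown.

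A reader might also infer that a child whose plates fused before consent drops out as no longer growing. That is only one reading. The definition in Section 9.3.2.7 is undated, closed is an allowed epiphyseal status, and the Safety Exposed Paediatric Population in Section 9.7.1 is defined by age. Judging the status afresh at each visit would remove every PPC case at closure, which can hardly be intended. The analysis plan may settle the date; it was not available for this review.

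Other limits also stand. The 12–18 month figure applies to chronic-only dosing, and the protocol does not call it the period of highest risk. Children consenting by month 12 have the window covered prospectively, as far as routine care provides. Whether interim images exist depends on local label and practice. PPC is not among the outcomes compared between cohorts, and unexposed children also have only one retrospective growth-status value (Table 4, note i).

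These points narrow the concern without removing it. A closure that nobody recorded as a diagnosis has no second route of capture, and the event route depends on sites reading an unnamed item into the row.

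**Conclusion.** The restriction is real and is stated consistently in Table 3 and Section 9.2.7.1. Its effect is conditional. For children consenting more than 12 months after first intake, part or all of the typical PPC window has no serial growth-plate data: 50% at month 15 and 100% from month 18, assuming uniform onset and chronic-only dosing. A diagnosed PPC remains collectable, though through a row that does not name it. An undiagnosed closure is at best bracketed between first intake and Baseline, and may be missed if growing-child status is judged at Baseline.

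The number of cases affected is unknown, because the interval from first intake to consent is not given. With roughly 6 to 11 PPC cases expected in total under the assumptions above, even a few with poorly documented onset would matter for a descriptive safety endpoint. The change is worth making because it is cheap and cannot be made at the analysis stage.

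**What to change.** 1. Remove note p from the growth-status and Tanner rows of Table 3. Align Sections 9.2.7.1 and 9.3.2.7 so that all available values from first marketed intake to Baseline are collected, as for linear height.
2. Name PPC explicitly in the retrospective important medical events row and on its form, matching Section 9.3.2.6 for unexposed participants.
3. State that growing-child status for the PPC and growth summaries is judged at the index date: first marketed intake for exposed participants, consent for unexposed participants.

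The cost is some additional retrospective chart entry and a repeating form in the case report form; no new assessment is required. Exposed children would then have denser retrospective growth-status data than unexposed children. That asymmetry should be noted if growth status is ever compared between cohorts.

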**PAGE 43 OF 287** 

 Table 4
 Schedule of Assessments: Unexposed Participants

Assessment/Procedure	Retrospective Period * (12 Months before baseline)	Baseline Visit	Follow-Up Visits (as per routine clinical practice[a])/ End of Study Visit [j]
Clinic visit or telephone/video contact visit		X	X
Informed consent [b]		X	
Inclusion/exclusion criteria		X	
Baseline demographics		X	
Physical examination [c,d]	X [i]	X	X
FOP history	X		
Growth status assessment (bone age, knee height and epiphyseal status) [d,e]	X [i]	X	X
Tanner staging	X [i]	X	X
Linear height and weight [d]	X	X	X
Vital signs [d,f]	X [i]	X	X
medications	X	X	X
Concomitant surgery and non-drug therapies	X	X	X
Spirometry and DLCO test [d,g]	X [i]	X	X
CAJIS [d]	X [i]	X	X
Movement mobility history (including flare-ups)	X		
Movement mobility changes (including flare-ups)		X	X
Medical events of special interest	X	X	X
Participant Questionnaires:			1
FOP-PFQ assessment [h]		X	X
PROMIS Global Health Scale [h]		X	X
FOP assistive devices assessment [h]		X	X

CAJIS=Cumulative Analogue Joint Involvement Scale; DLCO=Diffusion Capacity of the Lung for Carbon Monoxide; FEVi=Forced Expiratory Volume in one second; FOP=Fibrodysplasia Ossificans Progressiva; FOP-PFQ=FOP-Physical Function Questionnaire; FVC=Forced Vital Capacity; HEENT= head, eyes, ears, nose and throat; PROMIS=Patient-Reported Outcomes Measurement Information System;.

**PAGE 44 OF 287** 

- \* Retrospective period starts 12 months preceding the signed informed consent but only from the time the child has reached the age of 8 years for girls and 10 years for boys.
- a Follow-up Visits are recommended every 6 months.
- b If participant <18 years (or the legal age of consent in the jurisdiction in which the study is taking place), assent and parent or legally authorised representative consent will also be required.
- c This includes a general assessment, dermatologic, lymph nodes, HEENT, chest, cardiac, abdomen, limb/extremities, musculoskeletal, neurologic and other.
- d Not expected in the context of a telephone/video visit.
- e Collected for growing children.
- f Vital signs to be collected are respiratory rate, blood pressure and heart rate.
- g Spirometry obtains the lung function parameters of observed and % predicted FVC and FEV1 and the absolute and % predicted FEV1/FVC ratio. The DLCO test obtains observed and % predicted DLCO which provides information on the efficiency of gas transfer from alveolar air into the bloodstream.
- h Paper-based patient-reported questionnaires.
- i Closest available value to 12 months preceding signed informed consent.
- j Previously unexposed participants starting palovarotene and remaining in FOPal should follow the exposed naïve participants schedule from the first marketed palovarotene intake (See Table 2 and Section 9.2.8).

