# 9.1 Registry Study Design

FOPal is an observational, prospective and retrospective registry study designed to collect and assess real-world safety data on paediatric and adult participants with FOP exposed to palovarotene and secondly to describe the effectiveness of palovarotene in exposed participants. Additionally, key safety outcomes (i.e. flare-up episodes, growth and bone fractures) will be descriptively compared in participants with FOP exposed and unexposed to palovarotene enrolled in the FOPal registry.

Exposed and unexposed participants will be recruited in countries/sites willing to participate and where palovarotene is registered/marketed. For exposed participants, the decision to prescribe palovarotene will be made prior to and independently of the decision to enrol the patient in the FOPal registry study.

Participants who started palovarotene treatment before the implementation of the registry study in their country may also be enrolled. All participants who received at least one dose of palovarotene treatment before enrolling in the registry study (i.e. signing the informed consent) will be considered non-naïve. In such context, some data will be collected retrospectively from the first dose of marketed palovarotene intake. A schematic representation of the different data collection scenarios is shown Figure 2.

Figure 2 Schematic representation of the different scenarios applied for prospective and retrospective data collection from participants enrolled in the FOPal registry

The schedule of assessments in Table 2 and Table 3 describes the type of data collected for exposed naïve and non-naïve participants, respectively, from the first dose of marketed palovarotene intake. The schedule of assessments in Table 4 describes the type of data collected for unexposed participants from up to 12 months before the ICF signature. The details are described in the Section 9.2.7.

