**PAGE 48 OF 287** 

#### REGISTRY STUDY PROTOCOL: VERSION 8.0: DATE 16 APRIL 2025

- Concomitant medications;
- Concomitant surgery and non-drug therapies;
- Spirometry and DLCO test;
- CAJIS for FOP:
- Movement mobility history including flare-ups (over the past 12 months prior to the Baseline Visit);
- Movement mobility changes including flare-ups (from Baseline Visit);
- Medical events of special interest (over the past 12 months prior to the Baseline Visit);
- FOP-PFQ (the adult form should be used for participants 15 years and older and for participants under 15 years old, there is a self-completed paediatric form (developed for participants 8 to 14 years old) and a proxy completed paediatric form (developed for participants 5 to 14 years old));
- PROMIS Global Health Scale (the adult form should be used for participants 15 years and older and for participants under 15 years old, there is a self-completed paediatric form (developed for participants 8 to 14 years old) and a proxy completed paediatric form (developed for participants <15 years old));
- FOP assistive devices assessment.

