### 9.3.2.1 Demographic and Baseline Characteristics

The FOPal registry study will collect the following data at the Baseline Visit if available:

- Baseline demographics including date of birth, gender and race, where permitted;
- Reason for absence of treatment for unexposed participants, when available;
- Physical examination (only if clinic visit) including a general assessment as well as dermatologic, lymph nodes, HEENT, chest, cardiac, abdomen, limb/extremities, musculoskeletal, neurologic and other assessments (as per routine clinical care) for all participants at the Baseline Visit, at the first marketed palovarotene intake for exposed non-naïve participants and at the Follow-up/End of Study Visits;
- Medical or surgical history, excluding FOP-related history, within the 12 months before the signed informed consent date for exposed naïve or unexposed participants and within the past 12 months prior to the first marketed palovarotene intake for exposed non-naïve participants;
- FOP history including the date of symptom onset, date of diagnosis by a physician, method of diagnosis, date of genetic test if performed and type of FOP genetic variant;
- Number of flare-ups over the past 12 months prior to the first marketed palovarotene intake and until the signed informed consent date for exposed non-naïve participants or 12 months preceding the signed informed consent date for exposed naïve or unexposed participants;
- Movement mobility history within the 12 months before the signed informed consent date for exposed naïve or unexposed participants and over the past 12 months prior to the first marketed palovarotene intake and until the signed informed consent date for exposed non-naïve patients. The latter includes locations, mobility impact start date, change in movement, change in extra bone growth, symptoms if preceded by a flare-up event and causes.

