#### Flare-ups

At Baseline, the investigator will ask the participant how many flare-ups they experienced over the past 12 months. At each Follow-up Visit, the investigator will ask the participant how many flare-ups they experienced since the last visit.

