# Flare-ups

The number of flare-ups over the past 12 months prior to baseline and since the last visit will be presented for each visit.

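### The Table 4 note shortens the look-back for the youngest unexposed children, while the rest of the protocol asks for and reports a full 12 months

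*Protocol*

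**What the plan says.** Two readings of the unexposed look-back stand in the current text.

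**Shortened window.** The asterisked note under Table 4 states: "Retrospective period starts 12 months preceding the signed informed consent but only from the time the child has reached the age of 8 years" (girls), and 10 years for boys. Section 9.1 is compatible with this, since it describes data "collected for unexposed participants from up to 12 months before the ICF signature".

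**Full 12 months, no age limit.**
- Section 9.2.7.2, Baseline Visit list for unexposed participants: "Movement mobility history including flare-ups (over the past 12 months prior to the Baseline Visit".
- Section 9.3.2.1, number of flare-ups at Baseline: "12 months preceding the signed informed consent date for exposed naïve or unexposed participants".
- Sections 9.3.2.6 and 9.3.2.7 (Fractures): medical events of special interest and fractures over the 12 months before consent.
- Section 9.3.2.8 (Flare-ups): "At Baseline, the investigator will ask the participant how many flare-ups they experienced over the past 12 months".
- Section 9.7.3.4 (Flare-ups), on reporting: "The number of flare-ups over the past 12 months prior to baseline and since the last visit will be presented for each visit". No adjustment for a shorter window is stated.

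**Exposed cohort.** Note l of Table 2 (naïve) and note l of Table 3 (non-naïve) take flare-ups over 12 months before consent and before first marketed intake respectively. Note f of each table takes a height from 6 to 12 months earlier. None of these notes has an age limit.

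**The concern.** The age limit applies to controls only. A girl who consents at 8 years 3 months has 3 months of history if she is unexposed and the note is followed. She has 12 months if she is exposed and naïve. Her 3-month count would still be tabulated as a 12-month count.

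Three outputs are exposed to this:
- the baseline flare-up count in Section 9.7.3.4;
- the annual change from Baseline in the number of impacted locations (Sections 9.3.1.2 and 9.7.3.3), where a short Baseline window would be set against full follow-up years;
- the change from Baseline in height velocity (Sections 9.3.1.2 and 9.7.3.4), because Table 4 places earlier heights inside the shortened period.

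Sites can also resolve the contradiction differently, so the same tabulated variable could cover different periods at different sites.

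**Working it through.** The protocol gives no figure that depends on this window, so there is nothing to reproduce. The check is window arithmetic.

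**Inputs.** Minimum of 33 unexposed participants, about half of them paediatric, so 33 / 2 = 16.5 (Section 9.5). Eligible paediatric ages are 8 to under 18 for girls (10 years wide) and 10 to under 18 for boys (8 years wide) (Section 9.2.2.1). Velocity needs two heights 6 to 12 months apart (Section 9.7.3.4, Growth Status).

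**Assumptions.** Ages are spread evenly over the eligible range, the event rate is constant within a child, and adults and children have the same mean count. The protocol gives none of these.

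**Window per child.** With m months since the 8th or 10th birthday at consent, look-back = min(12, m), and captured share = look-back / 12:

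| m (months) | Captured share of a 12-month count |
|---|---|
| 1 | 8% |
| 3 | 25% |
| 6 | 50% |
| 9 | 75% |
| 12 or more | 100% |

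For m even on 0 to 12, the mean window is 6 of 12 months, so affected children lose on average 50% of the count.

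**Number affected.**
- Girls: 1/10 = 10%. Boys: 1/8 = 12.5%.
- Equal sexes: (10% + 12.5%) / 2 = 11.25%, and 0.1125 × 16.5 = 1.9 children.
- Range from all girls to all boys: 1.65 to 2.06 children.

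**Shortfall in the mean baseline count.**
- Paediatric controls: 0.1125 × 0.5 = 5.6% (range 5.0 to 6.25%).
- All 33: half of that, 2.8% (range 2.5 to 3.1%).

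**Sensitivity to the age assumption.** If 5% to 40% of paediatric controls fell in the first eligible year, 0.8 to 6.6 children would be affected. The shortfall would be 2.5 to 20% in paediatric controls and 1.25 to 10% in all 33.

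**Impacted locations.** Taking the Baseline value from the 12-month mobility history, a shortened window lowers it in the same direction. The percentage loss can be smaller than for flare-ups, because one location can be hit more than once in a year.

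**Height velocity.** If m is below 6, the earliest height inside the window is less than 6 months before consent, so no pair reaches the minimum spacing. That is half of the affected band: 1.9 / 2, about 1 child. An exposed naïve child of the same age can have a height from 6 to 12 months before Baseline under Table 2 note f.

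**After correction.** With a full 12 months, or with each flare-up count divided by the months covered, the expected shortfall in the flare-up count is 0% in every child.

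**The case against.** The strongest reply is that nothing is lost if the investigator asks the question in Section 9.3.2.8, because it covers 12 months. This stands. The understatement is conditional on a site applying the Table 4 note, and the firm finding is the contradiction.

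A reader might infer that the exposed-versus-unexposed comparison is biased in favour of palovarotene. The documents do not support that. The comparison in Section 9.7.3.4 covers annualised flare-up frequency, height velocity and z-scores, and fractures, with unexposed participants followed forward from consent. The look-back lies outside that follow-up. The listed propensity covariates are age, gender, time since the last flare-up and CAJIS total score; the 12-month count is not among them. A short look-back might limit what is known about time since the last flare-up, but the protocol does not say that covariate is taken from this window. Flare-ups have no change-from-Baseline endpoint, and mobility is not among the compared outcomes.

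It can also be said that the cut-off ages equal the inclusion ages, so restricting data to eligible age is a design choice. That is arguable, but the exposed cohort has the same inclusion ages (Section 9.2.1.1) and no such cut, and the other sections would still need correcting.

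Finally, these are routine-care data, missing values are expected (Section 9.8.4), and the analysis is descriptive. That limits the weight of the point but does not excuse labelling a shorter window as 12 months.

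**Conclusion.** The contradiction and the asymmetry between cohorts hold. Where the note is followed, controls in their first eligible year have an understated baseline flare-up count and an annual change in impacted locations that leans towards false worsening. Those in the first six months of that year have no Baseline height velocity.

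The size is small: about 2 of 16 to 17 paediatric controls, with a mean baseline count 5 to 6% too low in paediatric controls and 2.5 to 3% in all 33. These figures rest on evenly spread ages, a constant event rate, equal mean counts in adults and children, and every site following the note. The between-cohort comparison is not directly affected. Severity is minor.

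**What to change.** Remove the age limit from the Table 4 note for flare-ups, movement mobility history, medical events of special interest and linear height. The note then agrees with Sections 9.2.7.2, 9.3.2.1, 9.3.2.6, 9.3.2.7 and 9.3.2.8 and with the exposed naïve look-back. It would not make all cohorts identical, because Section 9.3.2.1 runs the non-naïve window from 12 months before first marketed intake up to consent.

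If the limit is kept, correct those sections instead, record the look-back start date, and annualise the flare-up count by the months actually covered. For shortened windows, do not present the change from Baseline in impacted locations as a 12-month comparison.

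The first option costs one footnote edit. The second costs corrections to several sections, one recorded date and one derived denominator. Neither adds visits.
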